Concomitant Medications		Conti	nuous from si	gning ICF until 30 days after last dose of study therapy		
Subsequent Anticancer Therapy					X	x
AESI, irAEs and SAEs	Continuous from signing ICF until 90 days after last dose of study therapy or resolution/stabilization					
Hematology 3,4	Х	C1D1	C2D1	C3D1 then Q6W (ie, at every other visit) and as clinically indicated	Х	
Chemistry ^{3,4}	Х	C1D1	C2D1	C3D1 then Q6W (ie, at every other visit) and as clinically indicated	Х	
INR, PT, PTT (or aPTT)	Х	As clinically indicated				
Thyroid Monitoring 3,5	Х	Q6W (±7D) and as clinically indicated				
Pregnancy Test ^{3,6}	≤2D before C1D1	Q12W (±14D)				

Confidential Page 20 of 109

Cutaneous, Subcutaneous and Nodal Lesion Measurement and Photographs ^{3,7}	Х	C1D1, C1D8, C1D15	C2D1, C2D8, C2D15	Day 1 of each Cycle	х	per SOC
Tumor Imaging ⁸	≤6W before C1D1	6 & 12W after C1D1, then Q12W thereafter. Crossover participants must have re-baseline imaging within 28D prior to administration of crossover C1D1 (i.e. first dose of anti-PD-1 therapy)				
Tissue Biopsy ⁹ All samples to be collected prior to dosing at the given timepoint	Prior to PV Immunization Booster	C1D8	C2D1	At the time of PD ± 1 week (per RECIST) Crossover Only: within 1 week prior to crossover C1D1, 1 week after crossover C1D1 (pre-dose, if applicable), 3 weeks (+7d; pre-dose) after crossover C1D1, and at the time of PD ± 1 week (per RECIST) on the crossover regimen		
Blood Collection ¹⁰ All samples to be collected prior to dosing at the given timepoint	Prior to PV Immunization Booster	C1D1, C1D8	C2D1	C3D1 and at the time of PD ± 1 week (per RECIST) Crossover Only: within 1 week prior to crossover C1D1, 1 week after crossover C1D1 (pre-dose, if applicable), 3 weeks (+7d; pre-dose) after crossover C1D1, and at the time of PD ± 1 week (per RECIST) on the crossover regimen		
Lerapolturev Administration ¹²		C1D1, C1D8, C1D15	C2D1, C2D8, C2D15	C3D1 and Q3W thereafter		
ARM 2: Anti-PD-1 Administration (pembrolizumab)		C1D1	C2D1 (if given Q3W)	C3D1 and Q3W or Q6W thereafter per pembrolizumab package insert		
Crossover from Arm 1 to Arm 2 13		If participant meets protocol-defined criteria				
Lerapolturev Shedding: Injected Lesion ¹⁴		C1D1 (post- injection), C1D4, C1D8, C1D15 (post- injection), C1D18	C2D1, C2D15 (post- injection), C2D18	C3D1		
Lerapolturev Shedding: Stool			C2D8 (±3D)			

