1.1. STUDY OVERVIEW

This multi-center, open-label, randomized, Phase 2 study will investigate the efficacy and safety of lerapolturev alone (Arm 1) or in combination with an anti-programmed cell death 1 (PD-1) inhibitor (Arm 2) in participants with unresectable, advanced anti-PD-1/L1 refractory melanoma. Following a 6-participant safety run-in period, up to approximately 50 participants with unresectable cutaneous melanoma who previously failed an anti-PD-1/L1-based therapy will be randomized 1:1 to receive either lerapolturev or lerapolturev plus an anti-PD-1.

As of December 10, 2021, the safety run-in was completed and a total of 17 participants had been enrolled. Upon review of the safety profile for lerapolturev administered as monotherapy or in combination with anti-PD-1 therapy, and in agreement with the Data Safety Monitoring Committee (DSMC), the protocol was amended to allow the total lerapolturev dose to be increased from 6 x 10^8 TCID₅₀/visit to a maximum of 1.6×10^9 TCID₅₀/visit, with up to 6 lesions injected per visit. The lerapolturev dosing schedule (referred to hereafter as once weekly (QW)) was also updated in this amendment to include weekly injections x 7 followed by either dosing every three weeks (Q3W) (lerapolturev monotherapy [Arm 1] or in combination with pembrolizumab [Arm 2]) or dosing every four weeks (Q4W) (combination with nivolumab [Arm 2]).

In Arm 2, anti-PD-1 therapy will be administered per the manufacturer's prescribing information concurrently with lerapolturev beginning Day 1. Participants enrolled in the safety run-in, or those randomized to Arm 1 (lerapolturev only), are allowed to crossover to Arm 2 for the following reasons: (1) disease progression per Response Evaluation Criteria in Solid Tumors (RECIST) 1.1, (2) once a partial response (PR) lasts at least 6 months, (3) after 26 weeks on study without RECIST-defined progression (ie, stable disease (SD) or unconfirmed PR or complete response (CR)). Those participants who crossover to Arm 2 may be required to repeat or continue the QW dosing, depending on when the crossover occurs, as shown in Table 1 (See Section 3.1.1 of the Study Protocol for additional information).

Table 1. Lerapolturev Injection Schedule After Crossover

Schedule of lerapolturev monotherapy injections at the time of crossover	Timing of when criteria for crossover are met	Recommended lerapolturev dosing schedule for combination

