Because lerapolturev is an immunotherapeutic administered by intratumoral injection, AESIs fall into 2 categories: (1) AEs related to lerapolturev administration (ie, injection site reaction [ISR]), and (2) AEs related to cytokine release syndrome [CRS] and immune effector cell-associated neurotoxicity syndrome [ICANS], which can occur when the body's immune cells release a bolus of inflammatory cytokines in response to an immunotherapy.

AESIs are collected through 90 days post last dose of study drug.

Immune-Related Adverse Events (irAEs)

Any adverse event affecting an organ system through an autoimmune or inflammatory mechanism, whereby the immune system is acting against normal tissue. The list of terms to identify irAEs is as

follows: (1) high level term (HLT): Colitis (excl infective); (2) HLT: Lower respiratory tract inflammatory and immunologic conditions; (3) HLT: Hepatocellular damage and hepatitis NEC; (4) HLT: Hypothalamic and pituitary disorders NEC; (5) HLT: Adrenal cortical hypofunctions; (6) HLT: Diabetes mellitus (incl subtypes); (7) HLT: Nephritis NEC; (8) HLT: Encephalitis NEC; (9) Preferred term (PT): Toxic epidermal necrolysis; (10) PT: Severe cutaneous adverse reaction; (11) PT: SJS-TEN overlap; (12) PT: Stevens-Johnson syndrome. Recommendations for study drug management in the event of an irAE are described in Protocol Section 5.5.

irAEs are collected through 90 days post last dose of study drug.

Concomitant Medications

Concomitant medications are those medications taken on or after the initiation of study drugs through 30 days post last dose of study drug. This definition includes medications started prior to initiation of study drugs and continuing concomitantly with study drugs.

Prior Medications

Prior medications are those medications taken and discontinued prior to initiation of study drugs.

Complete Response (CR)

A CR is defined by:

- disappearance of all target lesions AND
- disappearance of all non-target lesions AND
- all lymph nodes must be non-pathological in size (< 10 mm short axis) AND
- no appearance of new unequivocal lesions.

Partial Response (PR)

A PR is defined by:

- \geq 30% decrease in the sum of diameters of target lesions, taking as reference the baseline sum diameters AND
- non-CR / non-PD or not evaluated non-target lesions AND
- no appearance of new unequivocal lesions.

Stable Disease (SD)

Stable disease (SD) is defined by:

- non-PR / non-PD of target lesions AND

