- Participants who crossed over from lerapolturev monotherapy to lerapolturev + anti-PD-1 from treatment group assignment until death from any cause or last imaging, if participant is alive
- Participants who crossed over from lerapolturev monotherapy to lerapolturev + anti-PD-1 from time of crossover until death from any cause or last imaging if participant is alive

Disease Control Rate (DCR)

DCR is defined as the proportion of participants achieving confirmed CR, confirmed PR, or SD as best response.

Disease Control Rate-6 Months (DCR-6mo)

DCR is defined as the proportion of participants achieving confirmed CR for any duration, confirmed PR for any duration, or SD for ≥ 6 months as best response.

Treatment Period

Treatment period is defined as Cycle 1, Day 1 of study to the EOT.

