5.6.1.2. Primary Efficacy Analysis

The number of participants in each category of best overall response per RECIST v1.1 (confirmed CR, confirmed PR, SD, unconfirmed CR, unconfirmed PR, PD, non-evaluable (NE)) and ORR along with the associated exact 95% two-sided CIs using Clopper Pearson method will be computed within each treatment group and dosing schedule. A participants BOR will be determined based on Table 4.

Supportive data listings will also be provided.

Table 4 Best Overall Response When Confirmation of CR and PR are Required

First Timepoint	Second Timepoint	
Response	Response	Best overall response for ORR
CR	CR	CR
CR	PR	SD, PD or PR ^a
CR	SD	SD
CR	PD	SD
CR	NE or NA	SD
PR	CR	PR
PR	PR	PR
PR	SD	SD
PR	PD	SD
PR	NE or NA	SD
NE CD L	NE	NE

CR = complete response, PR = partial response, SD = stable disease, PD = progressive disease, and NE = not evaluable. a If a CR is truly met at first time point, then any disease seen at a subsequent time point, even disease meeting PR criteria relative to baseline, makes the disease PD at that point (since disease must have reappeared after CR). However, sometimes "CR" may be claimed when subsequent scans suggest small lesions were likely still present and in fact the patient had PR, not CR at the first time point. Under these circumstances, the original CR should be changed to PR and the best response is PR.

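### The SAP's partial-response definition leaves out participants whose non-target disease has cleared, and its rules for unconfirmed responses and six-month stable disease are incomplete

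*SAP*

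**What the plan says.** **Response categories.** SAP 3.2.6 defines CR by several joint conditions, the first being "disappearance of all target lesions AND". PR needs a fall of at least 30% in the sum of target diameters, no new lesions, and "non-CR / non-PD or not evaluated non-target lesions AND". SD needs "non-PR / non-PD of target lesions AND", no new lesions, and non-target disease that has not progressed or was not fully assessed. PD needs target growth, non-target progression or a new lesion.

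**Best response.** SAP 5.6.1.2 will count participants in these categories: "confirmed CR, confirmed PR, SD, unconfirmed CR, unconfirmed PR, PD, non-evaluable (NE". It then says "A participants BOR will be determined based on Table 4". In Table 4 a CR or PR followed by SD, PD or a missing or non-evaluable assessment has best response SD. DCR (SAP 3.2.6) counts confirmed CR, confirmed PR and SD.

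**Six-month disease control.** DCR-6mo counts confirmed CR of any duration, plus "confirmed PR for any duration, or SD for ≥ 6 months as best response". Protocol Table 1 schedules imaging at "6 & 12W after C1D1, then Q12W thereafter", with a re-baseline scan in the 28 days before crossover. SAP 1.1 lets Arm 1 and run-in participants cross over "after 26 weeks on study without RECIST-defined progression (ie, stable disease (SD) or unconfirmed PR or complete response (CR". Protocol 3.1.1 and footnote 13 to SAP Table 3 also say 26 weeks. Footnote 13 to SAP Table 2, the schedule that covers monotherapy, says 36 weeks.

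**The concern.** ORR is the primary efficacy endpoint, and Arm 2 QW is judged on whether the lower confidence limit exceeds 10%. With about 15 participants, one classification can decide that, so the definitions should place every possible assessment in exactly one category. The PR definition does not. It shuts out a participant whose response is better than the minimum for PR.

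The pattern is plausible here. Sites are asked to leave at least one target lesion uninjected where possible, and target lesions need not be injected lesions (Protocol 5.3 and 7.1). Injected non-target lesions could clear while uninjected targets only shrink.

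The other two gaps affect secondary endpoints. If unconfirmed responses can sit in two categories, two programmers following the same section can report different DCRs. If six months of SD has no start date, month length or crossover rule, DCR-6mo for monotherapy participants who cross over around week 26 is settled by choices not written down.

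**Working it through.** **1. Target PR with non-target CR, no new lesion, checked against each definition**
- CR: fails, because target disease remains.
- PR: the target and new-lesion conditions are met. The non-target condition fails, because the lesions were evaluated and their status is CR.
- SD: fails, because the target status is PR.
- PD: fails, because nothing has grown or appeared.

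A full grid of 4 target states, 5 non-target states (CR, non-CR/non-PD, PD, not evaluated, none present) and new lesions yes or no gives 4 × 5 × 2 = 40 combinations. Of these, 38 match exactly one category and 2 match none: the case above, and target PR with no non-target lesions at all. The second gap is softer, since a programmer might read absent lesions as not evaluated.

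The SAP does not say how an unmatched time point is coded. If it were set to NE, Table 4 would turn a PR followed by that time point into SD. A participant could then lose confirmation by improving.

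**2. Effect on the Arm 2 QW rule**

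The Clopper-Pearson limits for x responders of n are: lower = the 0.025 quantile of Beta(x, n − x + 1); upper = the 0.975 quantile of Beta(x + 1, n − x).
- x = 5, n = 15: 11.82% to 61.62%. This reproduces the 11.8% to 61.6% in SAP 3.1.
- x = 4, n = 15: 7.79% to 55.10%. The lower limit is under 10%.

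**3. Unconfirmed responses**

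Take PR at one assessment and SD at the next.
- By the category list: unconfirmed PR, separate from SD, so not in DCR as defined.
- By Table 4: SD, so in DCR.
- ORR: non-responder either way.

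Each such participant moves DCR by 1/15 = 6.7 percentage points in a group of 15.

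**4. Six-month SD before a week-26 crossover**

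Days are counted from Cycle 1 Day 1, with a month of 30.4375 days (an assumption, since the SAP gives none). Six months is then 6 × 30.4375 = 182.6 days.
- Week 24: 24 × 7 = 168 days; 168 / 30.4375 = 5.52 months. Short of six.
- Week 26: 182 days = 5.98 months. Short by elapsed days. With the +1 of the SAP's Study Day it is 183 days = 6.01 months and passes. It also passes with 30-day months (180 days) or if six months means 26 weeks.
- Week 27, a nominal three-weekly visit: 189 days = 6.21 months. Passes.
- Week 36: 252 days = 8.28 months. Passes.

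For a crossover on day 182, the week-24 scan is 182 − 168 = 14 days old. It can serve as the re-baseline scan, so a later monotherapy scan may or may not exist. SAP 4.2 attributes efficacy assessments to the treatment in force at the time, which points to a week-36 scan after crossover counting under the combination. The explicit pre-crossover cut-off in SAP 5.6.1 is written for ORR only.

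**The case against.** **RECIST 1.1 governs.** The endpoint is defined per RECIST 1.1, Protocol 7.1 has response evaluated by those criteria, and best response is built from time-point responses. Nothing says the time-point calls will be re-derived by program from SAP 3.2.6. This stands. A reader might infer that the SAP wording removes responders from ORR; the documents support only that it could, if applied literally. The wording still needs correcting. Protocol 8.5 gives the SAP precedence over the protocol's statistical text, and SAP 5 has outputs checked for consistency with the plan.

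**Table 4 is the stated rule for best response.** On that reading the longer list is only a display breakdown, and DCR includes unconfirmed responses. This is the more natural reading, but Table 4 labels its result as being for ORR and the list sets SD beside the unconfirmed categories, so one clarifying sentence is needed.

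**The week-24 scan is not the last possible one.** Re-baseline imaging is part of the schedule, crossover is optional, and the trigger is after week 26. This largely stands. A reader might infer that Arm 1 participants who cross over around week 26 cannot reach six months of SD; the re-baseline scan contradicts that. A reader might also infer a bias towards the combination. The documents do not establish one: handling of post-crossover data for DCR-6mo is unstated, one crossover text says 36 weeks, and no formal comparison of the arms is planned (Protocol 8.3).

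**Conclusion.** The gap in the PR definition is real on the text and bears on the primary endpoint. Its size is conditional: if response is derived literally, and if one of exactly five Arm 2 QW responders has this pattern, the result moves from 5/15 (lower limit 11.8%) to 4/15 (7.8%) and misses the 10% threshold. The documents give no frequency for the pattern.

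The treatment of unconfirmed responses is an inconsistency within SAP 5.6.1.2. It can change DCR and possibly DCR-6mo, but not ORR.

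For DCR-6mo the supported conclusion is limited. The fixed week-24 scan cannot by itself establish six months of SD before a week-26 crossover (it would only if a month were 28 days). The result for these participants depends on re-baseline scan timing and on undefined conventions. No size or direction can be given, because the documents do not say how many will be in SD at week 24, when they will cross over, or when they will be rescanned. The 26-week and 36-week crossover texts contradict each other and must be reconciled.

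**What to change.** Amend the SAP before database lock:

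1. **PR.** Change the non-target condition to: non-PD or not all evaluated non-target lesions (including no non-target lesions at baseline), and CR criteria not met. This follows the SAP's own SD rule. The last clause keeps CR and PR exclusive.
2. **Best response.** State that Table 4 governs DCR as well as ORR, and show unconfirmed CR and PR as a sub-row of SD.
3. **DCR-6mo.** Define the date from which SD is counted, the length of a month and the day-count rule. Say whether assessments after crossover may contribute, and how to classify a participant whose last scan before crossover falls short of six months. Apply the same rules in every arm. Keep the protocol's threshold of at least six months: accepting SD at week 24 instead would redefine the endpoint to about 5.5 months.
4. **Crossover timing.** Reconcile footnote 13 to SAP Table 2 (36 weeks) with SAP 1.1, footnote 13 to SAP Table 3 and Protocol 3.1.1 (26 weeks).

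The cost is a few lines of text and a check of the response programs. No new data are needed.

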Statistical Methods	The primary endpoint for measuring anti-tumor activity will be ORR, based on RECIST 1.1, which will be summarized as the overall number (%) of participants with CR or PR in each treatment arm, along with 95% confidence interval (CI). Participants will be analyzed based on the treatment arm to which they were randomized, as well as by lerapolturev dose/schedule (ie, QW and Q3/4W). Other endpoints will be summarized by descriptive statistics, as appropriate. Further details for these and other analyses will be described in the statistical analysis plan (SAP).
Determination of Sample Size	Sample size was determined based on feasibility and logistical considerations. Based on an estimated sample size of 15 participants in Arm 2 receiving lerapolturev QW in combination with anti-PD-1, five objective responses are needed for the 95% confidence interval (CI) to be above 10% (33% ORR; 95% CI: 11.8% to 61.6%), which would indicate the combination has antitumor activity in this anti-PD-1 resistant population. See Section 8.3 for additional details regarding sample size determination.
Study Duration	Up to approximately 24 months (104 weeks)

Confidential Page 18 of 109

^Criteria for Crossover

- radiologic disease progression per RECIST v1.1 (progression does not need to be confirmed prior to crossover)
- has not had progression or confirmed partial response per RECIST v1.1 by week 26 on study
- partial response ≥ 6 months in duration

Confidential Page 19 of 109

Table 1. Schedule of Assessments for Lerapolturev Monotherapy or Lerapolturev + Pembrolizumab

NOTE: Cycle length for lerapolturev monotherapy or lerapolturev + pembrolizumab is 3 weeks. Lerapolturev is administered weekly during Cycles 1 & 2 and every 3 weeks thereafter on the days indicated in the table below. Refer to the table below for the timing of other study assessments to be completed within each cycle.

	Screening Period	o		EOT Visit ¹⁵	Survival Follow- up ¹⁶	
Study Procedure ³		Cycle 1	Cycle 2	≥ Cycle 3		
	(≤ 28D prior to C1D1)		+3W (+7D)	Q3W (+7D)	≤28D after last treatment	
Informed Consent ¹	X					
Medical History	X					
Physical Exam ^{2,3}	X	C1D1	C2D1	Day 1 of each Cycle	X	
Vital Signs ³	Х	C1D1, C1D8, C1D15	C2D1, C2D8, C2D15	Day 1 of each Cycle	X	
ECOG Performance Status ³	Х	C1D1	C2D1	Day 1 of each Cycle	Х	
PV Immunization Booster ¹	≥1W, but ≤6W before C1D1					
Adverse Events		Conti	Continuous from signing ICF until 30 days after last dose of study therapy			

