not to aid in the response of the tumor. If the lesion(s) treated is being followed for evaluation by RECIST (target or nontarget lesion), then "not evaluable" should be reported in the eCRF for this lesion at subsequent disease assessments following palliative radiotherapy or surgery. Participants requiring palliative radiation may continue receiving study drug until documented disease progression (radiographic or clinical) if, in the Investigator's opinion, the participant is continuing to receive clinical benefit and they meet the requirements described in Section 6.2. However, for participants who have not had disease progression at the time of the need for palliative radiation therapy or surgery, the requirement for intervention will be regarded as disease progression in the study's analyses and will be entered as such in the eCRF.

The following medications are also not permitted:

- Non-protocol specified investigational drugs.
- Use of topical corticosteroids with occlusive dressings.
- Anticoagulant use the day prior to, day of and the day following lerapolturev injection. Warfarin use is not allowed at any time during study participation. Antiplatelet agents, such as aspirin, clopidogrel, etc., are not considered anticoagulants for the purposes of this study and are allowed.
- Live virus vaccines (beyond lerapolturev)
 - Examples of live virus vaccines include, but are not limited to, measles, mumps, rubella, varicella/zoster, yellow fever, rabies, and typhoid vaccine.
 - Seasonal influenza vaccines for injection are generally killed virus vaccines and are allowed; however, intranasal influenza vaccines (eg, FluMist[®]) are live attenuated vaccines and are not allowed.

COVID-19 Vaccination:

Vaccination against COVID-19 is allowed on study, provided the vaccine is not based on a live virus (eg, the Johnson and Johnson single-dose vaccine or AstraZeneca vaccine). While on study, it is recommended that participants vaccinated with non-live virus vaccines (eg, mRNA-based vaccines) receive the vaccine at least 14 days before or after lerapolturev administration, if possible. The COVID-19 vaccine should be given in an anatomic area as far as possible from melanoma lesions that were recently injected with lerapolturev or that are planned for future injection. Participants receiving a COVID-19 vaccine based on a live virus may begin Cycle 1, Day 1, once they are at least 4 weeks removed from vaccine administration.

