- 3. Procedures and/or Assessments unless otherwise specified should occur on D1 of each Cycle. Any assessment or procedure scheduled on the same day as lerapolturev and/or anti-PD-1 administration should always precede receipt of study treatments. Note that laboratory assessments (eg, hematology, chemistry, thyroid monitoring) may be done up to 2 calendar days prior to Day 1 of the cycle.
- 4. Hematology and Chemistry: Blood draws for hematology and chemistry occurring on the same day as study treatment should be collected prior to lerapolturev injection and/or prior to anti-PD-1 infusion (as applicable). Hematology should include hemoglobin, white blood cell (WBC) count with differential and platelet count. Chemistry measured in serum should include the following: LDH, glucose, calcium, sodium, potassium, bicarbonate, chloride, BUN, creatinine, total protein, albumin, alkaline phosphatase (ALP), aspartate aminotransferase (AST), alanine aminotransferase (ALT), total bilirubin, amylase, and lipase.
- 5. Thyroid Monitoring: Should include TSH, free T4, and free T3.
- Pregnancy Test: A pregnancy test (urine-based allowed) must be performed for all female participants of childbearing potential during Screening (≤ 2 days of lerapolturev injection) and approximately every 12 weeks while on study. If a urine-based test produces an equivocal result, a serum-based test should be performed.
- 7. Measurement of Cutaneous, Subcutaneous and Nodal Lesions: Measurement by ruler or caliper (along with photographs) should occur prior to lerapolturev administration to determine/verify lerapolturev injection volumes for each lesion. For timepoint response assessment of target lesions not visible by radiography, ruler/caliper measurement with photographs should be performed prior to lerapolturev injection.

CONFIDENTIAL Page 8 19 November 2024

Final Version 2.0

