- non-PD or not all evaluated of non-target lesions AND
- no appearance of new unequivocal lesions.

Progressive Disease (PD)

Progressive disease (PD) is defined by:

- \geq 20% increase in the sum of diameters of target lesions, taking as reference the smallest sum on study (this includes the baseline sum if that is the smallest on study) and an absolute increase of at least 5 mm OR
- unequivocal progression of non-target lesions OR
- appearance of one or more new lesions.

Duration of Response (DOR)

DOR is defined as time since a confirmed objective response (CR or PR) is first observed (ie, the scan date when the response originally occurred prior to confirmation) until unequivocal disease

progression (PD) or death, whichever occurs first. Participants will be censored at the date of the last imaging, if there is no date for PD or death.

Objective Response Rate (ORR)

ORR is defined as the proportion of participants achieving confirmed CR or confirmed PR.

Durable Response Rate (DRR)

DRR is defined as the proportion of participants with confirmed CR or confirmed PR lasting ≥ 6 months.

Overall Survival (OS)

OS is defined as time from start of treatment until death from any cause or last follow-up if participant is alive. Participants who are lost to follow-up will be censored at the last date of contact. The primary analysis will include the following subgroups:

- Participants who received lerapolturev monotherapy
- Participants who received lerapolturev + anti-PD-1
- Participants who crossed over from lerapolturev monotherapy to lerapolturev + anti-PD-1 from treatment group assignment until death from any cause or last follow-up, if participant is alive
- Participants who crossed over from lerapolturev monotherapy to lerapolturev + anti-PD-1 from time of crossover until death from any cause or last follow-up if participant is alive

Progression Free Survival (PFS)

PFS is defined as time (number of months) from start of treatment until date of documented radiologic disease progression or death due to any cause, whichever comes first. Participants not meeting this definition will be censored at the date of the last imaging. The primary analysis will include the following subgroups:

- Participants who received lerapolturev monotherapy
- Participants who received lerapolturev + anti-PD-1

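### SAP 3.2.6 times OS and PFS from assignment in a group defined by later crossover, and its PFS rules omit progression events that the plan counts elsewhere

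*SAP*

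**What the plan says.** SAP 3.2.6 gives a general rule for each endpoint and then lists four groups for the primary analysis.

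- **OS, general rule:** "OS is defined as time from start of treatment until death from any cause or last follow-up if participant is alive".
- **OS, crossover group, first entry:** "from treatment group assignment until death from any cause or last follow-up, if participant is alive".
- **OS, crossover group, second entry:** "from time of crossover until death from any cause or last follow-up if participant is alive".
- **PFS, general rule:** from start of treatment "until date of documented radiologic disease progression or death due to any cause, whichever comes first", with censoring at last imaging otherwise.
- **PFS, crossover group, first entry:** "from treatment group assignment until death from any cause or last imaging, if participant is alive". The second entry has the same end points, timed from crossover.

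The other two groups are those who received monotherapy and those who received the combination. The SAP does not say whether crossovers stay in the monotherapy group, leave it, or are censored at crossover.

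SAP Section 2 and protocol 2.1 start both clocks at treatment group assignment, not at start of treatment. SAP Section 11 puts every OS and PFS table and figure on the Efficacy Set, which under SAP 4.2 attributes treatment according to what the participant is receiving at each assessment. SAP Section 7 lists OS and PFS in the crossover subgroup among the analyses no longer to be done.

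The protocol synopsis (Statistical Methods) says "Participants will be analyzed based on the treatment arm to which they were randomized", and also by dose and schedule. Protocol 5.4 says that, for a participant without progression who needs palliative radiotherapy or surgery, "the requirement for intervention will be regarded as disease progression in the study's analyses and will be entered as such in the eCRF".

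**The concern.** Membership of the crossover group is decided after the clock has started. The routes in protocol 3.1.1 are progression, week 26 without progression or confirmed partial response, or a partial response lasting six months. Each requires the participant to be alive when it is reached. Time from assignment to crossover is therefore guaranteed survival (immortal time). A long curve for this group could be read as benefit from adding anti-PD-1 when none exists. The group is not small: at the December 2021 cutoff, 7 of 11 monotherapy participants had crossed over (protocol 1.2.2.2).

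For PFS the difficulty is different. Under the general rule, the progression that triggers crossover is already the event. The crossover entries do not name progression at all, so a programmer who followed them would produce something close to OS. Leaving out the palliative-treatment rule would likewise lengthen PFS in any group where such treatment occurs before documented progression.

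**Working it through.** The documents give no OS or PFS figure (no median, event count or hazard ratio), so there is nothing of the plan's to reproduce. The size below is an illustration under a null model in which crossover has no effect on survival.

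**Inputs from the documents**
- Scans at weeks 6 and 12, then every 12 weeks (schedules of assessments).
- Crossover on progression or at week 26 (protocol 3.1.1). The six-month partial-response route is not modelled.
- Crossover share 7/11 = 64% (protocol 1.2.2.2). This is a share of all treated at an interim cutoff. I use it as the probability of crossing among those alive when a route opens.

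**Assumptions not in the documents**
- True median OS 12 months (range 8 to 24); median time to progression 2.5 months; crossover two weeks after the progression scan or after week 26.
- Two death models: (a) death independent of progression, both times exponential; (b) every death follows progression, with exponential survival after progression scaled so that the overall median is unchanged.

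**Hand check, model (a).** With a constant hazard the remaining median at crossover is again 12 months. The earliest crossover is week 8 (8 × 12/52 = 1.8 months), giving a median of 1.8 + 12 = 13.8 months from assignment. The latest is week 28 (6.5 months), giving 18.5. The group median must lie between them.

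**Simulation, 400,000 participants per scenario, median OS in months**

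| True median | Model | Crossed over, from assignment | Excess over all monotherapy | Crossed over, from crossover |
|---|---|---|---|---|
| 12 | (a) independent | 16.1 | 4.1 | 12.0 |
| 12 | (b) deaths follow progression | 13.2 | 1.2 | 8.8 |
| 8 | (a) / (b) | 12.0 / 9.4 | 4.0 / 1.4 | 8.0 / 4.9 |
| 24 | (a) / (b) | 28.2 / 25.2 | about 4.1 / 1.2 | 24.1 / 21.0 |

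The excess is positive in every row, about 1 to 4 months. The from-crossover median has no immortal time. Under (b), however, most of the group starts that clock after progression, so the median falls below 12. It cannot be set beside curves timed from assignment.

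**PFS.** With true median OS 12, crossovers have a median PFS of 2.8 months (the week-12 scan, 12 × 12/52) when progression counts. Read literally, with death as the only event, the median becomes 13.2 months under (b) or 16.1 under (a). About 76% to 81% of simulated crossovers already had documented progression before crossing; the literal wording discards that event.

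**Palliative treatment, side by side.** Protocol 5.4 counts the need for it as progression in the analyses. SAP 3.2.6 counts documented radiologic progression or death. SAP Section 7 does not list the difference.

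**The case against.** Much can be said for the plan. OS and PFS are secondary, summarised by Kaplan-Meier only, and protocol 8.3 states that no formal hypothesis is tested on additional comparisons. The activity criterion is the Arm 2 QW response rate, which none of this touches. The SAP already provides a from-crossover OS curve, which removes the immortal time. The general PFS rule, Section 2 and SAP 5.6.2.1 all count progression, so the crossover entries may be loose drafting. A palliative-treatment progression is to be entered in the eCRF and could reach the analysis as recorded progression. Section 7 may mean that the crossover analyses will not be run.

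These points limit the finding but do not remove it. The assignment-timed entries remain in 3.2.6 as part of the primary analysis of each endpoint, and the SAP does not say which section prevails.

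Three stronger readings are tempting and are not supported:

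- **A false gap of roughly 8 to 11 months between crossovers and those who never crossed.** The SAP defines no never-crossed group. A gap of that size also needs death to be independent of progression: 16.1 against 6.5 months, a gap of 9.6, when the true median is 12. If deaths follow progression it is 13.2 against 10.1, a gap of 3.1. The independent model puts 15% dead by week 12 (7% in the other), although entry requires a life expectancy above 12 weeks.
- **Caliper-documented progression is censored.** The SAP's definition of progressive disease is not tied to a modality, SAP 5.6.2.1 applies RECIST 1.1, and protocol 7.1 evaluates by imaging and/or caliper. The SAP schedule footnote adds: "For timepoint response assessment of target lesions not visible by radiography, ruler/caliper measurement with photographs should be performed". The word radiologic in the PFS rule needs clarifying, no more.
- **Both endpoints are biased throughout.** Arm 2 as randomised, and Arm 1 as assigned with its crossovers kept in, do not carry the flaw.

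**Conclusion.** The concern holds in limited form. The OS group defined by later crossover and timed from assignment is biased upward by construction. The size, about 1 to 4 months over all monotherapy participants in these scenarios, rests on assumed survival and progression times and on how death relates to progression, so only the direction is firm. The PFS crossover entries contradict the SAP's own PFS definition. The protocol 5.4 progression rule has dropped out without being recorded. The clock start differs between SAP Section 2 and 3.2.6, and 3.2.6 conflicts with Section 7. Because no OS or PFS output is planned on the randomised groups, and treatment is attributed at each assessment, no planned curve provides a sound reference. The endpoints are secondary and descriptive, so this should be fixed but does not threaten the main conclusion.

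**What to change.** 1. Report OS and PFS by randomised arm within each dosing schedule (QW and Q3/4W), from one stated clock start. Keep Arm 1 crossovers in Arm 1 and show the safety run-in separately.
2. Delete the two crossover entries timed from assignment.
3. Keep the from-crossover curves, labelled descriptive and not for comparison with other groups. For PFS the event is progression against the crossover re-baseline, or death.
4. Apply the protocol 5.4 progression rule in the SAP PFS definition, or list its removal in Section 7.
5. Reconcile 3.2.6 with Section 7 on whether crossover OS and PFS are analysed.
6. As a clarification only, refer to progression per RECIST 1.1 and to the last evaluable tumour assessment, so that caliper assessments are plainly included.

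The cost is SAP wording and reprogramming of two endpoints. No new data are needed. Crossover OS and PFS will look shorter.
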